Phase 1 Patients with a percutaneous core biopsy demonstrating invasive carcinoma or ductal carcinoma in situ will undergo contrast enhanced bilateral breast MRI in the prone position, as is the current clinical standard at Dartmouth. At the time of surgical consultation, patients with palpable invasive breast cancer or DCIS who desire breast surgery will be invited to be a part of the study. Prior to surgery these patients will undergo a contrast enhanced supine MRI and an optical scan. The optical scan will be done with the patient in the surgical position. This image will be used to adjust the MRI image obtained preoperatively into a highly accurate representation of the breast and the MRIdefined tumor mass to correspond to the position of the patient at the time of surgery. This image will be projected on a screen above one side of the patient's head for easy viewing. This image display will indicate the distances at a particular radian (measured in terms of clock hours and minutes) from the nipple to all aspects (cranial, caudal, medial, lateral) of the tumor. The image display will also indicate the distances from the skin to the tumor and from the tumor to the chest wall. Measurements of the distance from the nipple to these edges of the palpable tumor at specified, measured radians will also will be made by the surgeon and will be compared to the optical scanner adjusted supine MRI images.

Phase 2. Patients with histologic evidence of invasive carcinoma or ductal carcinoma in situ will undergo bilateral breast MRI in the prone position, as is the current standard at Dartmouth. At the time of surgical consultation, patients with non-palpable breast cancers who desire breast conservation will be invited to be a part of the study. Consenting patients will undergo randomization, stratified by DCIS vs invasive cancer and for invasive lobular cancer vs invasive ductal cancer. Patients in Group W will undergo wire-localized partial mastectomy.

Patients randomized to Group S will undergo a contrast enhanced supine MRI and optical scan, followed by partial mastectomy using the image guidance system we developed and verified in Phase I (19).

Standard radiologic images (mammograms, ultrasounds, prone MRI images) will be available to the surgeon at the time of surgery for all patients. Patients in Group W, the usual care group, will undergo standard of care breast conserving surgery as practiced at our institution for non-palpable breast cancers.

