Patients in Group S will undergo a supine MRI at a convenient time within a week of surgery. They will have an optical scan of the breast surface while on the OR table on the day of surgery. Using the methods described and validated in Phase I, the scan data will be used to adjust (coregister) the supine MRI image volume obtained pre-operatively into a highly accurate representation of the breast and MRI defined tumor mass at the time of surgery. This coregistered image will be projected on a screen for easy viewing by the surgeon. A hand held, sterile stylus pointer will be tracked during surgery and will allow the surgeon to point to a specific location on the breast and see exactly where that point is on the screen image display. The image display will indicate the distances from the nipple to all aspects (cranial, caudal, medial, lateral) of the tumor, as well as the distances from the tumor to the skin and from the tumor to the chest wall. Guided by the coregistered image information the surgeon will mark on the surface of the breast the extent of resection. The sterile stylus probe may be used during the procedure to relate points in the surgical field to their corresponding location on the coregistered supine MRI image. The surgeon will resect the breast tumor volume that is identified by the image guidance system.

The surgical specimens will be water displaced to determine their volume. The specimen will then be inked by the surgeon with 6 different colors to orient the specimen (black: deep, blue: superficial, green: caudal, orange: cranial, yellow: lateral and red: medial), and will undergo specimen mammography. Specimens will then be sent to Pathology. Margins for invasive cancers will be considered positive if cancer cells are present at the edge. Margins will be considered positive for DCIS if there are tumor cells < 1 mm from the edge. The distance to the nearest margin will be determined in all cases.

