Our senior breast Pathologist, [name], has performed a detailed analysis of the surgical margins for patients who had a core biopsy which was positive for cancer or DCIS and then underwent partial mastectomy at Dartmouth in the year 2005. A total of 125 patients with invasive ductal carcinoma were identified: 31 (25%) had positive margins. Twenty six of 53 patients undergoing partial mastectomy for DCIS had positive margins (45%). Overall, 57/178 patients (32%) had positive margins. A two-thirds decrease in the positive margin rate (i.e., from 32% to 11 percent or less) would be clinically meaningful. The primary analysis will consist of computing the positive margin rate observed in the two groups and comparing them with a chi-squared test. Based on a chi-squared test with a significance level of 0.05 and a power of 80%, a sample size of 69 patients will be required in each group.

We will adopt a sequential testing procedure to assure that possible increases in the expected margin rate are detected. After 10% of the patients are enrolled, or 7 in each group, an exact test for proportions will be applied. If proportion of positive margins is greater than 32% and the p-value for the test is less than 0.004, the trial will be stopped as possibly increasing the rate. This procedure maintains the significance level at 0.05 and the power at 80% using Pocock boundaries for the Lan and Demets alpha spending function.[20]

Annually at Dartmouth we care for approximately 300 patients with invasive ductal cancer and 100 patients with DCIS. Approximately ²/₃ of these patients (266) will undergo breast conserving surgery. Approximately ³/₄ of these patients will have non-palpable tumors (200). We anticipate that it will be possible to accrue one third (67) of these patients per year. Thus, we expect that it will take 2 years to complete accrual.

Secondary endpoints will be analyzed as follows. The mean specimen volume from Group S will be compared to the mean specimen volume from Group W using t - statistics. The concordance between lesion volumes identified on the supine MRI images and the prone MRI images will be evaluated through correlation and regression analysis.

Relevant data will be saved in Velos case report forms. The NCCC Safety and Data Monitoring Committee will monitor this trial quarterly.

Section 9. HUMAN SUBJECTS

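### The sequential rule is said to assure detection of more positive margins, but its only specified early look (7 per group, exact p < 0.004) stops the trial 0.3% to 5.8% of the time if Group S alone doubles from 32% to 64%

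*Combined protocol and SAP*

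**What the plan says.** Everything on the rule is in Sections 7 and 8.

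- Purpose: "We will adopt a sequential testing procedure to assure that possible increases in the expected margin rate are detected".
- Timing and test: "After 10% of the patients are enrolled, or 7 in each group, an exact test for proportions will be applied".
- Action: "If proportion of positive margins is greater than 32% and the p-value for the test is less than 0.004, the trial will be stopped".
- Error control: the level of 0.05 and the 80% power are said to be preserved "using Pocock boundaries for the Lan and Demets alpha spending function".
- Final analysis: a chi-squared comparison of the two groups at 69 per group, designed on a fall from 32% to 11%.
- Other monitoring: "The NCCC Safety and Data Monitoring Committee will monitor this trial quarterly". Section 9 also gives a cancer-center committee oversight of the trial's conduct.

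The plan does not name the exact test or its sidedness. It does not say whether the proportion set against 32% is that of Group S or of both groups together. It gives no later look or boundary, no margin criterion for the committee, and no probability of stopping under a raised rate.

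**The concern.** Group S is operated on without a localizing wire, so a higher positive-margin rate is the main harm that this rule was written to catch. A look at 14 patients with a threshold of 0.004 can react only to nearly extreme data. Of the 138 planned patients, 138 − 14 = 124 (90%) enrol after it. A committee member or ethics reviewer who takes the stated purpose at face value would overrate the protection those patients have. If Group S really ran at 64% against 32% and the trial went to full size, about 0.32 × 69 = 22 extra patients in Group S would have positive margins.

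**Working it through.** **Inputs.** From Sections 7 and 8: 7 per group, p < 0.004, reference rate 32% (57/178), target 11%, 69 per group, level 0.05, power 80%. Assumed: Group W at 32%, Group S at various raised rates, and margin results in hand at each look.

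**1. The plan's own figures reproduce.**

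Sample size, with mean rate 0.215 and difference 0.21:

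n = [1.960·√(2·0.215·0.785) + 0.842·√(0.32·0.68 + 0.11·0.89)]² / 0.21² = 58.9

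With continuity correction: (58.9/4)·[1 + √(1 + 4/(58.9·0.21))]² = 68.1, rounded up to 69. So the 0.05 is two-sided.

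Threshold, Pocock-type spending at 10% information: 0.025·ln(1 + 0.1(e − 1)) = 0.00396. Using 0.05 in place of 0.025 gives 0.0079. The 0.004 therefore fits one tail of a two-sided 0.05.

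**2. Outcomes that stop the trial at 7 per group.** Enumerating all 8 × 8 outcomes, the plausible readings reduce to five stopping regions (S count vs W count):

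- A. Two-sided Fisher: 7 vs 0 only (6 vs 0 gives p = 0.0047).
- B. One-sided Fisher, two-sided Barnard or two-sided Boschloo: A plus 7 vs 1 and 6 vs 0.
- C. One-sided Barnard or Boschloo: B plus 7 vs 2 and 5 vs 0.
- D. One-sample test of Group S against 32%: 7 of 7 (6 of 7 gives p = 0.0055).
- E. Both groups pooled against 32%: 10 or more of 14 (p = 0.0029).

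**3. Chance of stopping at S = 64%, W = 32%.**

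- A: 0.64⁷ × 0.68⁷ = 0.0440 × 0.0672 = 0.30%.
- B: A + 0.0440 × 0.2215 (7 vs 1) + 0.1732 × 0.0672 (6 vs 0) = 2.43%.
- C: B + 0.0440 × 0.3127 (7 vs 2) + 0.2922 × 0.0672 (5 vs 0) = 5.77%.
- D: 0.64⁷ = 4.40%.
- E: sum over totals of 10 or more = 5.68%.

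Range over the five regions at other Group S rates, W = 32%:

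| Group S rate | Lowest | Highest |
|---|---|---|
| 40% | 0.01% | 0.7% |
| 50% | 0.05% | 1.9% |
| 64% | 0.3% | 5.8% |
| 80% | 1.4% | 21% |
| 90% | 3.2% | 48% |
| 100% | 6.7% | 60% (100% under D) |

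**4. The whole procedure.** Early look taken as one-sided Fisher, then the continuity-corrected chi-squared test at 69 per group. Harm is declared at S = 64% with probability 2.4% early + 93.2% final = 95.6%; at S = 50%, about 50%; at S = 40%, about 12%.

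**5. What later harm-only looks would do.** Exact recursion over all counts, early look kept, one-sided Fisher of S against W, W = 32%. Stopping probabilities:

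| Added looks (per group) | S = 64% | S = 50% | S = 40% | No difference | Any false conclusion, no difference |
|---|---|---|---|---|---|
| None (early look only) | 2.4% | 0.6% | 0.2% | 0.04% | 3.3% |
| 35, at 0.05 | 83% | 39% | 12% | 2.9% | 5.5% |
| 17, 35, 52, at 0.05 | 94% | 57% | 22% | 6.0% | 8.1% |
| 17, 35, 52, at 0.025 | 91% | 46% | 13% | 2.9% | 5.3% |

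The last column adds harm stops, final harm findings and final benefit findings. In every row the false-positive rate for benefit is 1.65% and power at S = 11% is 81% (both with continuity correction).

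**The case against.** The strongest reply is that detecting is not the same as stopping early. The plan also has a final two-group test, which would show a doubling nearly always. That stands, and it limits the point: a reader might infer that the trial could finish without noticing a doubled rate, and the documents do not support that. The shortfall at a doubling is in early protection. For smaller rises the whole procedure is weak as well (50% and 12% above).

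Second, the sentence can be read as a statement of purpose, and the 64% benchmark is not the plan's. Both are fair. But no rate below 100% makes stopping at this look certain under any reading, and the plan gives no figure from which a reader could learn that.

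Third, protection exists elsewhere. The committee reviews quarterly and nothing bars it from acting on margins. Phase 2 opens only if the Phase 1 accuracy criterion is met. Standard images "will be available to the surgeon at the time of surgery for all patients", and specimens undergo mammography. So it would be wrong to infer that patients are unmonitored. None of these supplies a margin criterion or a later look.

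Fourth, the pooled reading is not a test of S against W. If both groups rose to 64% it would stop 39% of the time, but that is not an effect of the new technique.

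**Conclusion.** The point holds as one about early stopping. The plan claims a protective property that its only specified early look does not have: 0.3% to 5.8% for a doubling in Group S alone, across every reading tried. The figures rest on Group W at 32%, on assumed Group S rates, and on margin results being available at the look.

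A reader might go further and infer that the 0.004 threshold is an error, or that the benefit comparison or sample size is compromised. Neither follows. The threshold and the 69 per group both reproduce, and a look that stops only for harm does not inflate false claims of benefit. This is a matter of accurate description and patient protection. It should be fixed, but it does not threaten the primary result.

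**What to change.** 1. **Needed.** Replace the sentence on assured detection with one saying that the early look can catch only a gross early failure. Name the exact test, the groups or proportion set against 32%, and the sidedness. State the look's sensitivity (under 6% for a doubling in Group S alone, with Group W at 32%) and that the final test gives no early protection. Cost: a few sentences.

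2. **Recommended, optional.** Add one or more harm-only comparisons of Group S with Group W at existing quarterly reviews, and report their operating characteristics. The schedules in the table are examples; number, times and thresholds are for the sponsor and committee to set. The pathology data are already collected ("The distance to the nearest margin will be determined in all cases"). At the expected 67 patients per year, 35 per group falls near month 70/67 × 12 = 12.5. Cost: a paragraph and one to three 2 × 2 tables. The downside is a false harm stop when the groups do not differ: about 3% with one look at 0.05 or three at 0.025, and about 6% with three at 0.05. None of the examples reliably finds a small increase (12% to 22% at S = 40%).

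3. **If looks are added.** Confine the significance-level statement to the false-positive rate for benefit, which does not change, and report the harm-side error separately. The total chance of a false conclusion would rise from 3.3% to between 5.3% and 8.1%, so an unqualified claim that the 0.05 level is preserved could not stay. Power at S = 11% remains 81%.

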A limitation of all of these MRI studies is that the MRI exams are performed with the patient prone and the breasts in a pendant position, which is markedly different than the position of the breast when the patient is supine on the Operating Room table. The spatial information the surgeon receives from the prone MRI about the site of the tumor in the breast is hard to mentally translate into the actual site of the tumor in the breast of a supine patient prepared for surgery. Of particular interest is a recent Japanese study that evaluated resections based on supine MRI in 24 patients with DCIS and compared them to 28 patients who had prone MRI and wire localized resections (18). The positive margin rate was lower in the supine MRI group (12% vs 39%, p=0.03) and the volume of breast tissue removed was less (27 vs 57 cm3, p=0.001). In this study the supine MRI image was correlated to the position on the OR table by taking plain xrays in the OR and lining up a metallic button on the surface of the breast with a clip left at the time of biopsy.

Section 2. OBJECTIVES

We propose to use a novel technique (optical scanning) to correlate the supine MRI image to the surgical position in the OR and then to confirm and extend the Japanese study described above. In the first phase of the study, 5-25 patients with palpable invasive breast cancer will undergo pre-operative supine MRI and optical scanning in the surgical position. The purpose of this phase will be ensure that the images created from the optical scanner-adjusted supine MRI images closely correspond to the location of the palpable tumors in these breasts. All patients will then have their tumor resected using the standard method of either palpation or image guided wire localization.

In the second phase of the study, patients with non-palpable invasive breast cancer or DCIS who desire breast conservation will be randomized to either a usual care group, or a group receiving a supine MRI in addition to conventional imaging (mammogram and prone MRI) and undergoing breast cancer resection without the wire localization technique.

The primary objective will be to determine whether the addition of supine MRI to conventional imaging with mammography and or sonography and prone MRI will result in a lower positive margin rate in patients undergoing breast conserving surgery.

Our secondary objectives will be to determine:

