- whether there are differences between the two groups in the volume of breast tissue removed.
- 2. whether diagnostic information obtained from a supine MRI is equivalent to that obtained from the prone MRI.

Section 3. ELIGIBILITY CRITERIA

Inclusion Criteria Phase 1

- 1. Age > 18 years
- 2. Histologic diagnosis of palpable invasive breast cancer or ductal carcinoma in situ
- 3. Patient desire to undergo breast surgery
- 3. Patients will have provided informed consent to participate, documented by their signature on the study consent form
- 4. The cancer enhances on breast MRI imaging.

Inclusion Criteria Phase 2

- 1. Age > 18 years
- 2. Histologic diagnosis of invasive breast cancer or ductal carcinoma in situ
- Determination by the surgeon that the neoplasm is non-palpable. A patient with a palpable hematoma from core biopsy, but a non-palpable neoplasm, will be eligible for study
- 6. Patient desire to undergo breast conserving surgery
- 7. Patients will have provided informed consent to participate, documented by their signature on the study consent form. The process of informed consent will be documented in the medical record and a copy of the signed consent form will be given to the patient.

Exclusion Criteria (Phases 1 and 2)

- Absolute contraindication to MRI, including presence of implanted electrical device (pacemaker or neurostimulator), aneurysm clip or metallic foreign body in or near eyes
- 2. Severe claustrophobia
- Contraindication to use of gadolinium based intravenous contrast, including life threatening allergy or compromised renal function (creatinine > 2.0)
- 4. History of median sternotomy
- 5. Pregnancy (Patient attestation that they are not pregnant will be acceptable, as per standard policy for MRIs at DHMC)
- 6. Multicentric breast cancer, defined as two or more tumors in different quadrants of the breast.

An eligibility worksheet will be completed for each patient prior to enrollment and will be signed and dated by the surgeon investigator.

Section 4. TREATMENT PLAN

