At the end of patient accrual, prone and supine MRIs from patients in Group S will be separately interpreted by two radiologists. The cases will be divided in halves. One radiologist will initially interpret half of the supine and half of the prone MRIs, the other will initially interpret the other half. After a 6-week interval, each Radiologist will interpret the other half of the images. Concerning lesions on each study will be identified, and then a comparison will be made between the supine and prone images to determine if lesions identified on the supine images are concordant with the number and size of lesions identified on the prone images.

Section 5. POTENTIAL TOXICITY

Supine MRIs are administered according to standard-of-care practice for prone breast MRI and represent no more additional risk than would be experienced by women receiving these exams as part of their (non-research) breast care. The risk of contrast enhanced MRI is very low, reflecting the minute risk of life threatening allergy and development of nephrogenic sclerosis related to gadolinium based intravenous contrast. Patients deemed to be at higher risk for gadolinium induced nephrogenic sclerosis because of compromised renal function will not be eligible for participation. Patients who experience a significant allergic reaction to gadolinium based intravenous contrast at the time of their clinical prone MRI will also be considered ineligible for study participation.

Optical scans will be performed using a GO!Scan 3D optical scanner (Creaform, Levis, Quebec, Canada). This scanner will be able to scan the entire breast in 1 minute. It uses white light (LED) to form the image, like a flashlight. There are no anticipated risks associated with the use of this scanner.

Section 6. DRUG FORMULATION AND PREPARATION

Not applicable.

Version 5.6.14

Sections 7 and 8. Clinical ENDPOINTS AND STATISTICAL ANALYSIS

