The primary objective of the first phase will be to determine how closely the optical scan adjusted images of the tumor location correspond with the location as identified by intraoperative tumor palpation and measurement. Precise distances from the nipple to the superior, inferior, medial and lateral edges of the tumor will be taken from the adjusted MRI images and then marked on the patient's skin. The surgeon will then palpate the tumor and measure the distance between the palpable superior, inferior, medial and lateral tumor edges and the spots located by MRI. An adjusted image will be considered acceptable if all 4 image guided measurements are < 1 cm from the palpable tumor edge. We will enroll at least 5 patients on this phase of the study. We will move on to Phase II when 90% of the measurements in the previous 5 patients are acceptable, as defined above. If by technical modifications we cannot meet these criteria for moving to phase II after 25 patients the protocol will be closed.

The primary objective of the second phase is to determine whether the addition of supine MRI to conventional imaging with mammography and prone MRI will result in a lower positive margin rate in patients undergoing breast conserving surgery. Following informed consent and enrollment, patients will be assigned to usual care or usual care plus supine MRI. A permuted block randomization will be used within strata defined by DCIS and type of invasive cancer to achieve balance in treatment totals within strata. The positive margin rate in the two groups will be computed and compared using a chi-squared statistic.

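### Specimen volume is compared by a valid but unadjusted t-test that uses neither the randomization strata nor pre-randomization tumor size, which gives up some precision on this secondary endpoint

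*Combined protocol and SAP*

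**What the plan says.** Section 2 makes it a secondary objective to learn "whether there are differences between the two groups in the volume of breast tissue removed". Section 4 fixes the measurement: "The surgical specimens will be water displaced to determine their volume". Sections 7 and 8 give the analysis: "The mean specimen volume from Group S will be compared to the mean specimen volume from Group W using t - statistics". No covariate, stratum, model or transformation is named. The regression mentioned in the next sentence of that section concerns agreement between supine and prone lesion volumes, not the comparison between groups.

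The design holds information that this analysis leaves out:

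- **Strata.** Section 4 says "Consenting patients will undergo randomization, stratified by DCIS vs invasive cancer and for invasive lobular cancer vs invasive ductal cancer". Sections 7 and 8 add "A permuted block randomization will be used within strata defined by DCIS and type of invasive cancer".
- **Baseline imaging.** Under Section 4, Phase 2 patients "will undergo bilateral breast MRI in the prone position, as is the current standard at Dartmouth". This comes before the surgical consultation at which they are invited and then randomized.
- **Size readings.** The study's own reading of lesion number and size takes place after accrual and covers one group: "prone and supine MRIs from patients in Group S will be separately interpreted by two radiologists".
- **Enhancement.** Section 3 requires the cancer to enhance on MRI in Phase 1 but not in Phase 2.

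**The concern.** Volume tells the reader whether a fall in positive margins came with more or less tissue removed. Section 9 also lists smaller excisions among the potential benefits of the experimental arm. The trial is sized on margins, and no precision is stated for volume, so the interval around the volume difference will be whatever the analysis yields.

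Tumor size is a plausible predictor of how much tissue is removed: in Group S the resection follows the tumor volume shown by the guidance system. If size does predict volume, the plain t-test leaves explainable variation in the error term, and the interval is wider than it need be. That matters if the true difference is modest.

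The point has to be settled in advance. The documents do not ensure a comparable size value for Group W or provide for lesions that MRI does not show, and covariates chosen after the outcomes are known invite doubt about selection.

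**Working it through.** **1. The plan's own figure.** None is stated for volume. The 69 per group is for margins (32% vs 11%, alpha 0.05, power 80%). Two-sided, without continuity correction:

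n = [1.96·√(2·0.215·0.785) + 0.8416·√(0.32·0.68 + 0.11·0.89)]² / 0.21² = 58.9, so 59.

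With continuity correction: (58.9/4)·[1 + √(1 + 4/(58.9·0.21))]² = 68.1, so 69. The stated figure reproduces and is used below.

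**2. An SD for volume (assumption).** The only volume figures are in Section 1, for 24 and 28 patients: "the volume of breast tissue removed was less (27 vs 57 cm3, p=0.001". No SD or test is given. If the p-value came from a two-sided pooled t-test on 50 degrees of freedom:

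- t for p = 0.001 is 3.496
- SE = (57 − 27)/3.496 = 8.58 cm3
- SD = 8.58/√(1/24 + 1/28) = 8.58/0.278 = 30.8 cm3

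**3. Gain from adjusting for size.** With within-group correlation r between size and volume, residual SD = 30.8·√(1 − r²), and SE = residual SD·√(2/69). Unadjusted, SE = 30.8·0.170 = 5.24 and the half-width is 1.98·5.24 = 10.4 cm3. Power is from the noncentral t distribution; the equivalent number per group is 69/(1 − r²).

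| r (assumed) | 95% CI half-width, cm3 | Detectable at 80% power, cm3 | Power for 15 cm3 | Equivalent unadjusted n per group |
|---|---|---|---|---|
| 0 (t-test) | 10.4 | 14.8 | 81% | 69 |
| 0.3 | 9.9 | 14.1 | 84% | 76 |
| 0.5 | 9.0 | 12.8 | 91% | 92 |
| 0.7 | 7.4 | 10.6 | 98% | 135 |

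For the cited 30 cm3 difference, power is about 99% or more with or without adjustment.

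**4. Skewed volumes.** Simulated log-normal volumes, 69 per group, 25% true reduction, log tumor size as covariate. Ranges run over r = 0.3 to 0.7.

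| Coefficient of variation (assumed) | t-test | ANCOVA | t-test on log volume | ANCOVA on log volume |
|---|---|---|---|---|
| 0.6 | 80% | 83–95% | 85% | 88–99% |
| 0.8 | 57% | 61–77% | 66% | 71–92% |
| 1.0 | 40% | 43–57% | 52% | 56–80% |

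At r = 0.3 the covariate adds only about 3 to 4 points on either scale. Under the null all four methods rejected in 4.1–5.6% of trials.

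**5. Strata alone.** Let q be the DCIS share and k the DCIS–invasive difference in SDs. The share of variance explained is R² = q(1 − q)k²/[1 + q(1 − q)k²]. With q = 100/400 = 0.25 from the annual caseload in Sections 7 and 8:

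- k = 0.5: R² = 0.047/1.047 = 0.045, and the SE falls by 1 − √0.955, about 2%
- k = 1: R² = 0.1875/1.1875 = 0.158, and the SE falls by 1 − √0.842, about 8%

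**6. Validity of the planned test.** A separate simulation used stratified permuted blocks (assumed block size 4; strata shares 25/65/10%). The t-test's type I error was 4.7% with no prognostic effect and 3.8% with strata R² 0.10 plus size R² 0.40, so it is valid and becomes slightly conservative. For a 0.49 SD difference, adjustment raised power from 81% to 92% at total R² 0.30. At R² = 0 it cost almost nothing (80.4% vs 80.3%).

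**The case against.** The strongest reply is that nothing here is wrong. The t-test answers the stated objective, is unbiased and holds its error rate, and the endpoint is secondary. The gain depends on a correlation that no document gives: at 0.1 or 0.2, power for 15 cm3 moves only from 81.1% to 81.5% or 82.6%. Limiting Phase 2 to non-palpable, non-multicentric tumors may narrow the spread of sizes and weaken the correlation. The 15 cm3 example is half the cited difference; at 20 cm3 unadjusted power is already 97%. The SD is fragile too. The cited patients all had DCIS, the test behind the p-value is unknown, and 30.8 against a mean of 27 implies a coefficient of variation above 1 in that arm. With skewed volumes and a weak correlation, the log scale gains more than the covariate: at a coefficient of variation of 0.8, the log t-test has 66% power against 61% for raw-scale ANCOVA at r = 0.3.

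All of this stands as a limit on size. It makes the point optional; it does not show that the plan uses the available information. The log result does not displace the mean comparison as the lead analysis, because a ratio of geometric means answers a different question from the difference in means the plan asks about. It does support reporting log volume as a sensitivity analysis. Two practical criticisms should also be met in the wording: several volume results need one named lead, and more than one lesion in a quadrant needs a measurement rule.

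**Conclusion.** The concern holds as an efficiency point for consideration. The planned comparison is valid but uses neither the strata nor a size that could be known before allocation in both groups. Nothing elsewhere in the documents supplies the adjustment.

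The loss cannot be fixed from the documents. Under the assumed SD of 30.8 cm3 and correlations of 0.3 to 0.7, the unadjusted interval is about 5% to 40% wider than the adjusted one (10.4/9.9 = 1.05; 10.4/7.4 = 1.41). With a weaker correlation the loss is negligible, and it has no practical effect on power if the true difference is near 30 cm3. Most of any gain comes from size. Neither the margin analysis nor the 69 per group is affected.

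**What to change.** Prespecify, before outcome data are examined:

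- **Lead analysis.** ANCOVA of specimen volume on group, randomization stratum and centered baseline tumor size, reported as an adjusted mean difference with 95% CI. State that this result carries the conclusion on volume.
- **Size.** Take it from the clinical report of the pre-randomization prone MRI, in the same way in both groups, and not from the later study reading, which omits Group W. State which measurement is used when there is more than one lesion, and give a rule for lesions not visible on MRI, for example an indicator term.
- **Alongside.** Keep the planned unadjusted comparison of means. Add log volume (ratio of geometric means) as a sensitivity analysis, not a replacement.

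The cost is SAP wording and one size value abstracted per patient, including Group W. No patients, readings or procedures are added. The gain shrinks if many lesions are not visible: with 15% not visible and an indicator, raw-scale ANCOVA power in the skewed scenarios is about 82–94%, 58–75% and 43–54% at coefficients of variation of 0.6, 0.8 and 1.0. If size cannot be captured reliably, adjusting for the strata alone needs no new data but gains little.
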